### 3.3 Analysis population

The analysis population for the anaemia deferment study will include all eligible participants, while the analysis population for the ID/IDA study and the trial will include all eligible and consented participants.

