## 4 Administration of Study Treatment

Potential first-time donors will be asked if they are interested in participating in a study of the prevalence of ID and IDA and the impact of iron supplementation on haemoglobin levels and repeat donation. Those who express interest, consent to the study, and are eligible will be asked to return within 3 weeks. During this 3-week period a FBC, a peripheral blood film analysis, and a plasma ferritin measurement will be conducted, and participants will be classified as iron supplement participants (e.g., anaemic, ID, IDA) or otherwise (which we refer to as controls in this protocol).

Those found to be anaemic, ID or IDA will receive oral iron supplementation and nutritional counselling. The oral iron supplements will be ferrous sulphate 200mg (65mg Elemental iron). The iron supplements are already available at the Korle-Bu Teaching Hospital Pharmacy. The study principal investigators and study pharmacist will ensure the medicine is stored properly and dispensed only when needed for study participants. The following will be monitored and completed on a periodic basis to ensure the medicine is within study guidelines, pharmaceutical compliance, and manufacturer guidelines:

Drug Accountability Record.

Iron supplement Safety and Handling Sheet.

Controls will not be given iron supplementation at enrolment but will receive the standard practice of nutritional counselling for blood donors. If someone not given iron supplements at enrolment is found to be anaemic, ID or IDA at a follow-up visit that individual will receive iron supplements.

All study participants will have nutritional counselling, dietary advice, and for those

receiving iron, the need for iron therapy to be used consistently 3 days a week.

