#### Primary analysis

The analysis for the primary outcome of haemoglobin levels at 4 months will be conducted using a linear model with haemoglobin levels at 4 months as the response variable. It is unlikely that there is a need to transform the response variable as haemoglobin levels are usually symmetrically distributed with tails that decay at rates consistent with the normal distribution. However, if informal univariate assessments of normality (e.g., qq-plots) indicate strong departures from these expectations, the Box-Cox transformation will be used to select a transformation. The set of explanatory variables will be group membership (i.e., received iron supplementation at enrolment or not), screening haemoglobin, sex, and age. A 1-sided t-test for the regression coefficient associated with group membership will be conducted with a significance level of 0.025 to test the inferiority hypothesis. This analysis will exclude individuals who did not receive iron supplementation at enrolment but received it during follow-up due to changes in ferritin or haemoglobin values. The frequency of this will be closely tracked and if more than 10% of participants in the group initially not receiving iron supplementation receive iron supplementation during follow-up, alternative analysis approaches will be considered and presented to the DSMB.

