## 7.2.2 Secondary outcomes

### Secondary outcomes related to efficacy

Several secondary outcomes relate to the efficacy of iron supplementation. The treatment of those not requiring iron supplementation at enrolment but requiring iron supplementation during follow-up will be the same as for the primary outcome. These secondary outcomes include:

- Change in haemoglobin over 4 months (g/dl).
- Ferritin levels at 4 months (µg/L).
- Diagnosis of ID or IDA at 4 months (Yes or No).
- Attempt to return for donation within 6 months (Yes or No).
- Successful donation within 6 months (Yes or No).

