### Secondary analyses of secondary outcomes related to efficacy

The first two secondary outcomes that related to efficacy (i.e., change in haemoglobin over 4 months and ferritin levels at 4 months) will be treated as continuous variables and will serve as response variables in multiple regression models. It is anticipated that there will not be a need to transform the change in haemoglobin (however the Box-Cox transformation will be pursued if there is evidence for skewness), but it is anticipated that ferritin will need to be transformed. Usually logarithmic transformations are required to reduce the skewness of variables of this sort (i.e., measured by an ELISA), and this will be pursued, but other transformations may be more appropriate. The multiple regression models will include group membership, screening haemoglobin, screening ferritin (log transformed if substantial skewness is present), sex, and age. The remaining 3 outcomes that related to efficacy (i.e., diagnosis of ID or IDA at 4 months, attempt to return for donation within 6 months, and successful donation within 6 months) will be examined using logistic regression models with group membership, screening haemoglobin, screening ferritin (perhaps transformed), sex, and age as covariates. A significance level of 5% will be used to determine statistical significance of effects and 95% confidence intervals will be used to summarize effect sizes.

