## Appendix A. Schedule of Assessments

Assessment	Screening (Day -14 to 0)	Enrolment (Day 0)	Biweekly (Throughout)	Interim Visit 1 (Week 8-10)	Interim Visit 2 (Week 16-18)	Final Visit (Week 24)
NBSG Pre-Donation Assessment	X					X
Informed Consent	X					
Inclusion and Exclusion Criteria	X					
Demographics	X					
Full Blood Count and peripheral blood comment	X			X	X	X
Plasma Ferritin	X			X	X	X
Malaria Parasites Testing (RDT)	X	X		X	X	X
Nutritional Counselling		X		X	X	
Qualitative Assessment						X
Follow-Up Calls			X			
Return Blood Donation Status				X	X	X
Assessment for Adverse Events		X	X	X	X	X
Adherence Assessment (for those receiving supplemental iron)			X	X	X	X
RDT – Rapid Diagnostic Test						

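### The exclusion of controls who start iron is not limited to iron started before the 4-month sample, so a 4-month ID/IDA diagnosis removes the control who has it

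*SAP*

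**What the plan says.** - **Exclusion.** The rule in SAP 7.2.1 (Primary analysis) is to "exclude individuals who did not receive iron supplementation at enrolment but received it during follow-up due to changes in ferritin or haemoglobin values". Under Quantitative Data Analysis, the Protocol has the same rule. No cut-off date is given, and follow-up runs to 6 months.
- **Carry-over.** SAP 7.2.2 says the treatment of controls "requiring iron supplementation during follow-up will be the same as for the primary outcome". The outcomes covered include ferritin at 4 months and diagnosis of ID or IDA at 4 months. The Protocol says the same.
- **When controls get iron.** SAP section 4: a control "found to be anaemic, ID or IDA at a follow-up visit that individual will receive iron supplements". The Protocol (Follow Up Assessments) says such participants are offered iron. Under Screening failures it makes iron conditional on recommended care when Hb is below 10 g/dL at follow-up.
- **Visits.** Full blood count and ferritin are taken at 2, 4 and 6 months (SAP 1.2 Design; Appendix A places the second interim visit at weeks 16 to 18).
- **Model.** The binary efficacy outcomes "will be examined using logistic regression models with group membership, screening haemoglobin, screening ferritin (perhaps transformed), sex, and age as covariates" (SAP 7.2.2).
- **Safeguards.** SAP 7.2.3 puts the excluded controls back in the control group for the primary outcome. The Protocol requires, as a minimum, sensitivity analyses placing them in each of the two groups. Above 10% of controls starting iron, SAP 7.2.1 says "alternative analysis approaches will be considered and presented to the DSMB".

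**The concern.** The 4-month blood sample does two jobs for a control. It supplies the outcome, and it decides whether the control starts iron and so leaves the analysis. That iron starts after the sample, so it cannot have affected the value being discarded. An iron-arm participant with the same 4-month result is kept.

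At stake is a listed secondary efficacy comparison, ID or IDA at 4 months, which cannot be estimated as written. Read at face value, it would make iron look harmful even with equal true rates. The ferritin comparison loses its low tail in one arm only. The primary haemoglobin comparison is also affected, because some controls are selected on the response variable.

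**Working it through.** **1. The plan's own figure.** Margin 1.0, assumed true difference -0.3, SD 1.89, one-sided alpha 0.025, power 85% (SAP 2.4):
n = 2 × 1.89² × (1.960 + 1.036)² / 0.7² = 130.9, so 131 per arm and 262 in all. Allowing 10%: 131/0.9 = 145.6, so 146 per arm and 292. Both figures reproduce. They give the arm sizes used below.

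**2. The logic for ID/IDA.** The trigger for iron is anaemia, ID or IDA. The outcome is ID or IDA, so every case meets the trigger. On the SAP wording every observed control case at 4 months receives iron during follow-up and is excluded. Observed control cases are 0 at any true rate. A 6-month result can likewise remove a control whose 4-month values were normal.

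**3. Illustration.** True counts are assumed (the documents give none for 4 months), with 131 per arm. Controls analysed = 131 minus control cases. Fisher's exact test, two-sided, stands in for the planned logistic model:

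| True cases, iron / control | Analysed, iron v control | p |
|---|---|---|
| 3 / 3 | 3/131 v 0/128 | 0.25 |
| 5 / 5 | 5/131 v 0/126 | 0.06 |
| 7 / 7 | 7/131 v 0/124 | 0.015 |
| 13 / 13 | 13/131 v 0/118 | 0.0002 |
| 7 / 13 (iron better, true p=0.24) | 7/131 v 0/118 | 0.015, favouring control |
| 13 / 13, 3 control cases decline iron | 13/131 v 3/121 | 0.019 |

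**4. The logistic model.** With a zero cell in controls and cases in the iron arm, the likelihood keeps rising as the group coefficient grows. Fitting 13/131 v 0/118 without covariates, the log odds ratio stood at 9.4, 19.4 and 34.3 after 10, 20 and 35 iterations. Adding covariates does not remove the separation on group.

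**5. Primary outcome, unadjusted.** Take the SAP's margin model (normal, SD 1.89, half of donors anaemic) and an assumed between-visit correlation r. The share of controls below threshold at month 4 is arccos(r)/π. Their mean above threshold is 1.89·r·√(2/π) with all kept, and 1.89(1+r)/(2√(2π)) ÷ (1/4 + arcsin(r)/(2π)) after month-4 exclusion.

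| r | Share below | Mean, all kept | Mean, after exclusion | Shift (g/dL) |
|---|---|---|---|---|
| 0.95 | 10% | 1.43 | 1.64 | 0.20 |
| 0.90 | 14% | 1.36 | 1.67 | 0.32 |
| 0.80 | 20% | 1.21 | 1.71 | 0.50 |

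The SAP expects fewer than half to be anaemic. If 20% are, the shifts are 0.12, 0.18 and 0.27.

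**6. Primary outcome, adjusted for screening Hb.** This was simulated with 146 per arm, group means -0.3 apart, 50-90% of the iron arm anaemic and a control fall of 0-0.3 g/dL, all assumed. Month-4 exclusion lowered the group coefficient by 0.11-0.43 at r = 0.90-0.95 and by 0.43-0.71 at r = 0.80. For example, at r = 0.90, 70% anaemic and no control fall, it moved from +1.42 to +1.16. Non-inferiority was declared in every run of all 18 cases, with and without the exclusion.

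**7. Effect of the fix.** In one simulated draw of 146 controls at assumed ID/IDA rates of 2%, 10% and 30%, independent between visits, there were 3, 16 and 47 true cases at month 4. The SAP rule leaves 0, 0 and 0. Excluding only those who started iron before the draw leaves 3/141, 13/124 and 32/100.

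**The case against.** **The zero is not absolute.** This stands. It needs iron to be received. Under the Protocol's offer, a control who declines stays in, and iron is conditional when Hb is below 10 g/dL. Imputation (SAP 7.2.5) could also create cases among controls with no 4-month sample. The result is then a strong downward bias, as in the last row of the first table.

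**The p-values are illustrative.** This also stands: Fisher's test is not the planned analysis, and at low true rates nothing would look significant. The loss of control cases does not depend on the rates.

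**Other analyses help.** SAP 7.2.3 restores these controls for the primary outcome. SAP 7.2.2 reports ID/IDA incidence in controls and plans longitudinal GEE models for ID, IDA, haemoglobin and ferritin, with no exclusion stated. These are real but partial. The incidence is one-arm, and the GEE covariates are not given. The inverse-probability weighting does reach the secondary efficacy outcomes but is not said to restore anyone. None repairs the planned between-group ID/IDA comparison.

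**Stronger readings the documents do not support.**
- A reader might infer that the trial would fail non-inferiority. The bias does run that way, but no adjusted case changed the decision.
- A reader might see a contradiction with SAP 3.3, where "the analysis population for the ID/IDA study and the trial will include all eligible and consented participants". That is the overall population. The exclusion is disclosed for a specific analysis and allowed for in the sample size.
- A reader might say the 10% trigger leads nowhere defined. That fits the SAP, but the Protocol sets minimum sensitivity analyses.

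**Conclusion.** The point holds on the text for ID/IDA and ferritin at 4 months. As the SAP is worded, control ID/IDA cases at 4 months are removed by the result that defines them, the planned odds ratio has no finite maximum-likelihood estimate, and control ferritin is truncated at 15 µg/L. This rests on the mandatory wording in SAP section 4. Under the Protocol's wording it is a strong downward bias in the control rate, with size depending on how many controls do not take iron.

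For the primary outcome the direction is clear (control mean up, estimate moved against non-inferiority). The size rests on an assumed within-person correlation that the documents do not give. No effect on the non-inferiority decision is shown, so the case for change rests on the secondary outcomes and on the principle of not selecting the analysis set by the outcome, not on lost power.

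**What to change.** In SAP 7.2.1 and 7.2.2, and the matching Protocol paragraphs under Quantitative Data Analysis:

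- Limit the exclusion to controls who started iron before the 4-month blood draw.
- State that controls who start iron at or after that draw stay in the control group with their pre-iron 4-month haemoglobin, ferritin and ID/IDA diagnosis.
- State that selection on the 2-month result remains in the main analysis.

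In SAP 7.2.3:

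- Extend the sensitivity analysis that keeps all controls as enrolled to every secondary efficacy outcome.
- Carry over the Protocol's analysis placing these controls in each of the two groups.

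Making the all-controls-kept analysis primary is an estimand choice for the sponsor, not something this defect requires. It would replace the untreated comparator named in the SAP 2.4 null hypothesis, because controls starting iron at month 2 carry up to two months of iron into their 4-month values. A control with ID at month 2 that resolved on iron would also count as a non-case.

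The rule for giving or offering iron is not touched, although the SAP and Protocol describe it differently and should be reconciled. The cost is wording plus slightly more analysis work. No new data are needed, and the SAP allows updates until database lock.

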## 7.2.2 Secondary outcomes

### Secondary outcomes related to efficacy

Several secondary outcomes relate to the efficacy of iron supplementation. The treatment of those not requiring iron supplementation at enrolment but requiring iron supplementation during follow-up will be the same as for the primary outcome. These secondary outcomes include:

- Change in haemoglobin over 4 months (g/dl).
- Ferritin levels at 4 months (µg/L).
- Diagnosis of ID or IDA at 4 months (Yes or No).
- Attempt to return for donation within 6 months (Yes or No).
- Successful donation within 6 months (Yes or No).

### Secondary analyses of secondary outcomes related to efficacy

The first two secondary outcomes that related to efficacy (i.e., change in haemoglobin over 4 months and ferritin levels at 4 months) will be treated as continuous variables and will serve as response variables in multiple regression models. It is anticipated that there will not be a need to transform the change in haemoglobin (however the Box-Cox transformation will be pursued if there is evidence for skewness), but it is anticipated that ferritin will need to be transformed. Usually logarithmic transformations are required to reduce the skewness of variables of this sort (i.e., measured by an ELISA), and this will be pursued, but other transformations may be more appropriate. The multiple regression models will include group membership, screening haemoglobin, screening ferritin (log transformed if substantial skewness is present), sex, and age. The remaining 3 outcomes that related to efficacy (i.e., diagnosis of ID or IDA at 4 months, attempt to return for donation within 6 months, and successful donation within 6 months) will be examined using logistic regression models with group membership, screening haemoglobin, screening ferritin (perhaps transformed), sex, and age as covariates. A significance level of 5% will be used to determine statistical significance of effects and 95% confidence intervals will be used to summarize effect sizes.

### Secondary outcomes related to safety and feasibility

Other secondary outcomes related to the safety of iron supplementation, as listed below:

1. Acceptability of iron supplementation among participants as indicated by:
  - incidence of SAEs.
  - incidence of grade 3 or 4 AEs.
  - response to questions about known adverse reactions to iron supplementation.
2. Incidence of gastrointestinal adverse events.
3. Incidence of suspected malaria or bacterial infections.

### Secondary analyses of secondary outcomes related to safety and feasibility

To maximize the power to detect an association between group membership and safety outcomes, a composite of grade 3 and 4 AEs, SAEs, gastro-intestinal problems, malaria, and bacterial infections will be constructed and compared between the groups.

The frequency of this composite will be compared between groups using Fisher's exact test. Furthermore, logistic regression models will be fit with group membership, sex, and age as covariates and the odds ratio associated with group membership will be estimated along with a 95% confidence interval. These models will be parameterized so that an OR greater than 1 indicates that the intervention group has a higher incidence of negative outcomes. Components of the composite will also be investigated using a similar approach.

The questions about known side effects to iron supplementation ask: Has the participant experienced any of the following since the last visit (mark all that apply)?

- Unpleasant taste.
- Constipation.
- Dark tools.
- Nausea.
- Vomiting.
- Abdominal pain.
- Diarrhea.
- Other; specify.

The incidence of each of these outcomes over follow-up will be computed and logistic regression models will examine the impact of group membership, sex, and age on these outcomes. The odds ratio and a 95% confidence interval for the group membership variable will be used to summarize the association. Models which look at the incidence of any of these outcomes will also be examined and an odds ratio and 95% confidence interval will be used to summarize the relationship.

The incidence of ID or IDA will be examined among participants in the control group (who are not ID and do not have IDA at baseline by definition). These estimates will be in the form of events per unit time. The generalized estimating equation (GEE) version of Poisson regression will be used with the robust standard error. A model with just an intercept and an offset (for those without complete follow-up for the final analysis and for interim analyses) will be used to estimate the rate and models with the covariates age and sex will be used to test for sex and age specific differences. Age will be treated as a categorical variable in these models with ranges 17-20, 21-40 and greater than 40. Note that data from different subjects will be treated as independent in this model: GEE are being used here to account for potential overdispersion. The same approach will be used to examine the incidence of ID and IDA separately.

Adherence will be assessed by pill counting and administering adherence questionnaires. Adherence will be calculated as the percent of follow-up days/expected pill consumption days, participant did consume the pill. A similar analysis will be conducted based on dosage if more than 10% of participants have a change in their dosage during follow-up. We will also use a validated simplified self-report medication adherence measure with the following six items:

- Number of remaining pills (integer).
- Ever forgot to take the study medicine (Yes or No).
- Are you careless at times about taking the study medicine (Yes or No).

Sometimes if you feel worse, do you stop taking your study medicine (Yes or No).

How often have you not taken the study medicine in the last week (4 options: 0, 1 day, 2 days, 3 days).

Days missed taking pills in the last two weeks (integer).

These items will be summarized with counts and proportions.

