Adverse events will be recorded in the Adverse Events eCRF under the signs, symptoms, or diagnosis associated with them, accompanied by the following information (as far as possible):

- AEs will be assessed.
- Its relationship to the study treatment.
- Its duration (start and end dates) or if the event is ongoing, an outcome of not recovered/not resolved must be reported.
- The grade of the AE.
- Whether it constitutes a SAE.
- Action taken regarding with study treatment.

All AEs will be treated appropriately. Treatment may include one or more of the following:

- Dose not changed
- Dose Reduced/increased
- Drug interrupted/withdrawn.
- Its outcome (i.e., recovery status or whether it was fatal).

If the event worsens the event will be reported a second time in the eCRF noting the start date when the event worsens. For Grade 3 and 4 AEs only, if improvement to a lower grade is determined a new entry for this event will be reported in the eCRF noting the start date when the event improved from having been Grade 3 or Grade 4.

Adverse events (including lab abnormalities that constitute AEs) will be described using a diagnosis whenever possible, rather than individual underlying signs and symptoms.

Once an AE is detected, it will be followed until its resolution or the end of follow-up and an assessment will be made at each visit (or more frequently, if necessary) of any changes in severity, the suspected relationship to the interventions required to treat it, and the outcome. If an AE has not resolved by the end of follow-up for a participant, the outcome of the AE will be recorded as unknown.

Common adverse events associated with iron supplementation are minor and include:

- Unpleasant taste,
- Constipation
- Dark stools
- Nausea
- Vomiting
- Abdominal pain
- Diarrhoea.

Abnormal laboratory values or test results constitute AEs only if they fulfil at least one of the following criteria:

- they induce clinical signs or symptoms
- they are considered clinically significant
- they require therapy.

Clinically significant abnormal laboratory values or test results will be identified through a review of values outside of normal ranges/clinically notable ranges, clinically significant changes from baseline or the previous visit.

Follow-Up for AEs

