Several secondary outcomes relate to the safety of iron supplementation. To maximize the power to detect an association between group membership and safety outcomes a composite of SAEs, gastro-intestinal problems, malaria, and bacterial infections will be constructed and compared between the groups. The frequency of this composite will be compared between groups using Fisher's exact test. Furthermore, logistic regression models will be fit with group membership, sex, and age as covariates and the odds ratio associated with group membership will be estimated along with a 95% confidence interval. Components of the composite will also be investigated using a similar approach. The incidence of grade 3 or 4 AEs will be treated in a similar fashion. The frequency of responses to specific questions about known side effects to iron supplementation will be compared between the groups using logistic regression, controlling for sex and age. Each question will be investigated in addition to a response to any of the questions.

Since the treatment is not assigned at random there is a strong potential that confounders will introduce bias into the estimates of the treatment effects. As an attempt to remedy this, sensitivity analyses using inverse probability weighting will be conducted. If we use to represent group membership for participant i and Z_i is a vector of predictors for this participant, the first step of the analysis is to estimate the stabilized inverse probability of "treatment" weights W_i for subject i , $W_i = P(X_i = x_i)/P(X_i = x_i|Z_i)$. An estimate of $P(X_i = x_i|Z_i)$ can be obtained by logistic regression and $P(X_i = x_i)$ can be estimated by the sample proportion. One then uses these weights in a regression model to adjust for participant characteristics that differ between the groups.

The incidence of ID or IDA will be examined among participants in the control group (who are not ID and do not have IDA at baseline by definition). These estimates will be in the form of events per unit time. If someone is found to be ID or IDA and then resolves that person re-enters the risk pool for an event. To account for multiple events in the same individual, the generalized estimating equation version of Poisson regression will be used with the robust standard error if necessary. The same approach will be used to examine the incidence of ID and IDA separately.

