## 5 Safety Assessment

### Definitions

#### **Adverse Event (AE)**

An AE is any untoward or unfavourable medical occurrence in a study participant, including any abnormal sign (e.g., abnormal physical exam or laboratory finding), symptom, or disease, temporally associated with their participation in research. Only AEs potentially related to iron supplementation will be recorded as AEs.

At each follow-up visit all participants will be asked if they have experienced each item from a list of common adverse reactions to iron supplementation. Furthermore, the occurrence of additional AEs will be sought by non-directive questioning of the study participant at each visit during the study. AEs also may be detected when they are volunteered by the study participants during or between visits or through physical examination findings, laboratory test findings, or other assessments.

Adverse events will be recorded in the Adverse Events electronic case report form (eCRF) under the signs, symptoms, or diagnosis associated with them, accompanied by the following information (as far as possible):

AEs will be assessed.

Its relationship to the study treatment.

Its duration (start and end dates) or if the event is ongoing, an outcome of not recovered/not resolved must be reported.

The grade of the AE.

Whether it constitutes a SAE.

Action taken regarding with study treatment.

All AEs will be treated appropriately. Treatment may include one or more of the following:

- Dose not changed.
- Dose Reduced/increased.
- Drug interrupted/withdrawn.
- Its outcome (i.e., recovery status or whether it was fatal).

If the event worsens the event will be reported a second time in the eCRF noting the start date when the event worsens. For grade 3 and 4 AEs only, if improvement to a lower grade is determined a new entry for this event will be reported in the eCRF noting the start date when the event improved from having been grade 3 or 4.

Adverse events (including lab abnormalities that constitute AEs) will be described using a diagnosis whenever possible, rather than individual underlying signs and symptoms.

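### The safety composite has different components in the protocol and the SAP, and its gastro-intestinal component is undefined, so the result can depend on which source and which mild symptoms are counted

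*SAP*

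**What the plan says.** **Composite, protocol** (Data Analysis, Quantitative Data Analysis): "a composite of SAEs, gastro-intestinal problems, malaria, and bacterial infections will be constructed and compared between the groups". Grade 3 and 4 AEs stand outside it: "The incidence of grade 3 or 4 AEs will be treated in a similar fashion".

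**Composite, SAP** (7.2.2, secondary analyses of safety and feasibility outcomes): "a composite of grade 3 and 4 AEs, SAEs, gastro-intestinal problems, malaria, and bacterial infections will be constructed". It is compared by Fisher's exact test and by logistic regression on group, sex and age, with an odds ratio above 1 meaning more negative outcomes on iron. Both documents also analyse the components separately.

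**Gastro-intestinal terms.** Inside the composite both documents speak of gastro-intestinal problems, without a definition. The SAP's outcome list has "Incidence of gastrointestinal adverse events" as an item of its own, apart from responses to the symptom questions. The symptom checklist is introduced later in SAP 7.2.2: "The questions about known side effects to iron supplementation ask" about unpleasant taste, constipation, dark stools (printed with a typing error), nausea, vomiting, abdominal pain, diarrhoea, and an open other item. Each checklist item has its own planned logistic model.

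**Dark stools** also appear in the protocol's Safety Assessment, in the list headed "Common adverse events associated with iron supplementation are minor and include", and in the matching SAP section 5 list of adverse reactions.

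**Recording.** SAP section 5, like the protocol, states: "Only AEs potentially related to iron supplementation will be recorded as AEs". The same sections say that all participants are asked about the listed side effects at each follow-up visit. SAP 2.3 says that neither participants nor investigators are blinded.

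**The concern.** The two documents describe two endpoints. An analyst working from the protocol would build a four-part composite, and one working from the SAP a five-part composite. Neither analysis section remarks on the difference.

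The undefined gastro-intestinal component matters more. Two data sources could supply it, and each can tilt the comparison.

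- **AE records.** A symptom enters only if it is judged potentially related to iron. The control group starts without iron and everyone knows who takes it, so the same constipation or nausea is less likely to be recorded in a control.
- **The whole checklist.** This is asked alike of everyone, which removes the recording filter. It also brings in dark stools, which the plan itself lists as a common, minor effect of iron. With no grade threshold, one such report would weigh the same as an SAE or malaria.

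The composite is the comparison constructed to gain power for safety, and the safety profile is part of how the plan defines acceptability for the next phase. If the source and symptoms are chosen after the data are seen, that choice could decide whether the composite is significant.

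**Working it through.** **1. Component lists side by side**

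| Component | Protocol | SAP 7.2.2 |
|---|---|---|
| SAEs | in | in |
| Gastro-intestinal problems | in, undefined | in, undefined |
| Malaria | in | in |
| Bacterial infections | in | in |
| Grade 3-4 AEs | out, analysed separately | in |

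Both are current text.

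**2. Arm size.** The documents give no sample size or rates for the composite, so the arm size comes from the primary outcome. Inputs (SAP 2.4): margin 1.0 g/dL, SD 1.89, true difference -0.3, one-sided alpha 0.025, power 85%.

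n per arm = 2 × SD² × (z₀.₉₇₅ + z₀.₈₅)² / (margin - 0.3)² = 2 × 1.89² × (1.960 + 1.036)² / 0.7² = 130.9, rounded up to 131.

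This matches the plan, and the other four rows of Table 3 reproduce as well. Total 262 / 0.90 = 291.1, taken up to 292, or 146 per arm.

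**3. Effect of counting dark stools.** Let h be the rate of all other components, equal in both arms; d the rate of dark stools on iron; c the rate in controls. All three are assumptions. Treating dark stools as independent of the rest:

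- iron composite = 1 - (1 - h)(1 - d)
- control composite = 1 - (1 - h)(1 - c)

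Example with h = 20%, d = 20%, c = 0: iron 1 - 0.8 × 0.8 = 36%, control 20%, odds ratio (0.36/0.64)/(0.20/0.80) = 2.25.

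Rejection rate of Fisher's test at two-sided 5% (the default in SAP 2.5), by full enumeration, 146 per arm:

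| Dark stools, iron / control | h = 10% | h = 20% | h = 30% |
|---|---|---|---|
| not counted | 3.2% | 3.6% | 3.7% |
| 10% / 0% | 53% | 31% | 21% |
| 10% / 2% | 34% | 20% | 14% |
| 10% / 5% | 14% | 10% | 8% |
| 20% / 0% | 97% | 84% | 66% |
| 20% / 2% | 92% | 74% | 56% |
| 20% / 5% | 77% | 56% | 40% |

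Where dark stools are counted, nearly all rejections go against iron. With 131 per arm the 20% / 0% row becomes 96%, 79% and 60%.

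**4. AE-record route.** The direction follows from the recording rule and the lack of blinding: fewer recorded events in controls. The documents give nothing from which to calculate its size.

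**5. Grade 3-4 mismatch.** Adding these events does not by itself produce the signal in step 3, which comes only from the undefined gastro-intestinal term.

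**The case against.** The strongest reply is that nothing puts checklist answers into the composite. The SAP's outcome list keeps responses to the symptom questions apart from gastro-intestinal adverse events, and the checklist has its own paragraph and models after the composite. The checklist also contains unpleasant taste and an open item, so it does not read as a definition of gastro-intestinal problems. This stands. A reader might infer that, as written, one report of dark stools makes a participant a composite event; the documents neither include nor exclude it. A reader might also infer that the term is named three ways within the composite. It has one name there, and the other names belong to a separate outcome and to the checklist.

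Second, a significant composite need not mislead, because components and individual symptoms are analysed separately and no stopping rule depends on the composite. This also stands, and it limits the harm. It does not tell the analyst how to build the endpoint.

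Third, the rejection rates rest on assumed rates and are highest with no dark stools in controls. That is fair: 5% in controls lowers them considerably, as the table shows.

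Fourth, the protocol calls its analysis text a summary ahead of a detailed SAP, so the SAP's list could be taken to govern. That makes the mismatch easy to resolve but leaves the gastro-intestinal term undefined in both.

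Finally, the plan calls every listed symptom minor and does not single out dark stools as harmless. Leaving out dark stools and taste while keeping mild constipation is therefore a judgement, and a mild kept symptom would still weigh the same as an SAE.

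**Conclusion.** The concern holds in a limited form. The component lists conflict on grade 3-4 AEs, and the gastro-intestinal component lacks a symptom list, grade and source. Both available sources can tilt the comparison against iron: AE records through the relatedness rule without blinding, the whole checklist through dark stools.

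On the checklist route, with 146 per arm and other components equal at 10-30%, rejection is about 21-53% at 10% dark stools on iron and about 66-97% at 20%, if controls have none. With 5% in controls it is about 8-14% and 40-77%. If dark stools are not counted it is 3-4%. These figures show what the composite could do under assumed, independent rates; they do not predict what it will do.

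The documents do not support a claim that the composite will show false harm, or that infection and serious-event results would be hidden. It is one secondary safety analysis in a non-randomised pilot, and the planned component and item analyses would reveal the driver. A wording change before database lock is worthwhile and proportionate.

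**What to change.** 1. Use the SAP's five-part component list in both documents.
2. Derive the gastro-intestinal component from the visit checklist asked of all participants, as any report of constipation, nausea, vomiting, abdominal pain or diarrhoea.
3. Report dark stools and unpleasant taste only in the item-level models already planned in SAP 7.2.2.

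The cost is wording in the protocol and SAP, with no new data collection, and fewer composite events, hence less power for the composite. Two limits remain. Unblinded self-report can still differ between groups. The grade 3-4 component still comes from AE records, so the relatedness rule still affects that part, and the report should say so.
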